Amendment 02	[03-Jan-2023]	Global
Amendment 01	[16-Sep-2022]	Global
Original Protocol	[17-Jun-2022]	

Amendment 06 (16-Feb-2024)

Overall Rationale for the Amendment:

The protocol OG6219-P001-06 has been amended to omit the interim analysis CCI [REDACTED]. At the originally planned timepoint for the described interim analysis (CCI [REDACTED]) it is currently projected that all participants would be enrolled and randomized to treatment. Because the duration of time it will take to stop the study enrollment at this timepoint, the planned interim analysis CCI [REDACTED] is no longer relevant.

Section number and Change	Description of Change (the information added is shown in bold, and deleted information is shown as a strike-out)	Brief Rationale
Section 1.1 Synopsis; Section 1.2 Study Schema; Section 2.3.1; Section 2.3.1 Risk Assessment; Section 2.3.3 Overall Benefit Risk Conclusion; Section 4.1 Overall Design; Section 7.3 Criteria for Study Termination; Section 9.3 Sample Size Considerations; Section 9.4.1 General Considerations; Section 9.5 Interim Analysis; Appendix 2: Regulatory, Ethical, and Study Oversight Considerations	Removed interim analysis (IA) CCI .	From a timing perspective the planned IA CCI is no longer relevant as it projected that all participants would have been enrolled and randomized by the planned IA timepoint. Clarification for psychometric analysis.
Section 5.2 Exclusion Criteria	Exclusion criteria #9 Has a no history of malignancy (except basal cell or squamous cell skin cancer) before signing informed consent.	Clarification that this is an exclusion criterion.
Appendix 3 Clinical Laboratory Tests	Table 9 Protocol Required Safety Laboratory Tests Removed Hemosiderin analyte from urinalysis	CCI

TABLE OF CONTENTS

TITLE PAGE	1
PROTOCOL AMENDMENT SUMMARY OF CHANGES TABLE	3
TABLE OF CONTENTS	5
LIST OF TABLES	9
LIST OF FIGURES	10
1.0 PROTOCOL SUMMARY	11
1.1 Synopsis.....	11
1.2 Schema	20
1.3 Schedule of Activities	21
2.0 INTRODUCTION.....	28
2.1 Study Rationale	30
2.2 Background	31
2.3 Benefit/Risk Assessment.....	32
2.3.1 Risk Assessment.....	33
2.3.2 Benefit Assessment	37
2.3.3 Overall Benefit Risk Conclusion	38
3.0 OBJECTIVES AND ENDPOINTS	41
4.0 STUDY DESIGN.....	45
4.1 Overall Design	45
4.2 Scientific Rationale for Study Design.....	46
4.3 Justification for Dose	47
4.4 End of Study Definition	48
5.0 STUDY POPULATION	49
5.1 Inclusion Criteria	49
5.2 Exclusion Criteria	51
5.3 Lifestyle Considerations	55
5.4 Screen Failures	56

1.0 PROTOCOL SUMMARY

1.1 Synopsis

Protocol Title:

A Phase 2a/b, Randomized, Double-blind, Placebo-controlled, Parallel Group, Multicenter, Clinical Study to Evaluate the Efficacy and Safety of OG-6219 in 3 Dose Levels, in Women 18 to 49 Years of Age with Moderate to Severe Endometriosis-Related Pain

Registry ID IND Number – 154574
EU-CTR Number: 2022-501310-57-00

Rationale:

Current medical treatments for endometriosis-related pain (ERP) are sometimes inadequate and have safety and tolerability issues that can limit their use, often leading patients to have repeated surgical interventions. Therefore, there is a need for development of new ERP medical therapies. A local inhibition of estrogen production at the ectopic implants level, for treatment of ERP, such as OG-6219, a novel inhibitor of hydroxysteroid-17 β -dehydrogenase type 1 (HSD17 β 1), can potentially avoid the limitations and systemic liabilities of the current hormonal treatments.

The purpose of this global Phase 2a/b study is to determine the efficacy, safety, and tolerability of 3 dose levels of OG-6219 (CCI [REDACTED] twice a day [BID]) in pre-menopausal women between 18 and 49 years of age (inclusive), who have moderate to severe ERP. The primary efficacy endpoint will assess the efficacy of 3 dose levels of OG-6219 in change from Baseline Cycle (BC) in endometriosis-related overall pelvic pain (OPP) score (the weighted mean of the dysmenorrhea [DYS] pelvic pain score and the non-menstrual pelvic pain score [NMPP; pain associated with micturition, defecation, ovulation, intercourse]) during the Treatment Cycle 3 (TRC3) compared to Placebo. The secondary endpoints will assess the efficacy of OG-6219 utilizing the DYS score versus Placebo at BC versus TRC3, and the NMPP score in addition to dyspareunia at BC versus TRC3. The study will also collect data health-related quality of life (HRQoL) using the 30-item Endometriosis Health Profile (EHP-30). The pain score entered CCI [REDACTED] by each participant in the electronic diary (eDiary) must capture the worst pelvic pain (peak pain) corresponding to that day and should be entered at about the same time (before going to bed). Participants will make CCI [REDACTED] entries regarding the severity of their OPP, DYS, NMPP into the eDiary to capture the efficacy endpoints of interest. In addition, data on the pharmacokinetics (PK) of OG-6219 and its primary metabolite FOR-1011 will be collected. Evaluation of efficacy will be based on the mean OPP, DYS, and NMPP scores collected using an eDiary. Safety and tolerability are primary objectives; the endpoint includes adverse events (AE), serious adverse events (SAE), laboratory assessments, assessment of electrocardiograms (ECGs), vital signs, physical exams, effect on systemic

hormones, effect on bone, effect on endometrium based on transvaginal ultrasound and endometrial histology, and assessments using the mental health evaluation via the Columbia-Suicide Severity Rating Scale (C-SSRS).

Objectives and Endpoints:

Objectives	Endpoints
Primary Endpoints The following primary efficacy endpoint will be assessed comparing Group A (CCI BID), B (CCI BID), C (CCI BID) with Group D (Placebo)	

 To evaluate the efficacy of 3 dose levels of OG-6219 (Group A, B, C) versus Placebo (Group D) in reducing OPP during TRC3, as measured by a NRS in the eDiary 	
 Change from BC to TRC3 in the mean OPP score^a
The following primary safety endpoints will be assessed for Group A (CCI BID), B (CCI BID), C (CCI BID) and Group D (Placebo)	

 To evaluate the safety and tolerability of OG-6219 	
 Proportion of participants who experienced any AEs/SAEs Abnormalities in clinical laboratory assessments, vital signs, and physical examination Proportion of participants who prematurely discontinued study treatment due to AEs/SAEs
Secondary Efficacy Endpoints The following secondary endpoints will be assessed comparing Group A (CCI BID), B (CCI BID), C (CCI BID) with Group D (Placebo)	
1. To evaluate the efficacy of 3 dose levels of OG-6219 (Groups A, B, C) versus Placebo (Group D) in reducing DYS during TRC3, as measured by a NRS in the eDiary	
 Change from BC to TRC3 the mean DYS score
2. To evaluate the efficacy of 3 dose levels of OG-6219 (Groups A, B, C) versus Placebo (Group D) in reducing NMPP during TRC3, as measured by a NRS in the eDiary	
 Change from BC to TRC3 the mean NMPP score
3. To evaluate the efficacy of 3 dose levels of OG-6219 (Group A, B, C) versus Placebo (Group D) reducing dyspareunia during TRC3, as measured by a NRS in the eDiary	
 Change from BC to TRC3 in the mean dyspareunia score
4. To evaluate the daily use of Sponsor provided rescue medication taken for ERP at TRC1, TRC2, and TRC3	
 Change from BC to TRC1, TRC2, and TRC3 in the mean number of tablets of rescue medication for ERP Change from BC to TRC1, TRC2, and TRC3 in the proportion of days participant has used rescue medication for ERP

Objectives	Endpoints
5. To evaluate the change in the PGI-S Score at different time points	
 Change in PGI-S Score from C to CCI
6. To evaluate the change in the PGI-C Score in different time points	
 Percentage of participants with any improvement on the PGI-C at TRC1, TRC2, and TRC3
7. To evaluate the change in the EHP-30 domains CCI from BC to TRC3	
 Change from BC to TRC3 in the EHP-30 Domain Scores
Secondary Safety Endpoints	
8. To assess the incidence of clinically significant ^d changes from V1 to C in bone biomarkers: 
 CCI 	
 Mean change from V1 to C in bone biomarker levels
9. To assess the incidence of any clinically significant ^d changes in laboratory parameters from V1 to CCI	
 Proportion of participants with clinical parameters of significance from V1 to CCI
10. To assess vaginal bleeding pattern over the 3 menstrual cycles (TRC1, TRC2, and TRC3) as captured in the eDiary	
 Mean change from BC to TRC1, TRC2, TRC3 in the percentage of days with vaginal bleeding
11. To assess any potential change in the ECG parameters at CCI	
 ECG parameter changes at CCI
Secondary PD / PK Endpoints	
12. To assess the change from V1 to C in serum hormone ^b concentrations	
 Mean change from V1 to C in serum hormone levels
13. To assess any difference in serum hormone ^b concentrations at C between active treatment versus placebo	
 Serum hormone levels comparing Group A (CCI BID), B (CCI BID), C (CCI BID) with Group D (Placebo)
14. To assess any difference in serum hormone ^b concentrations at C between active treatment versus placebo	
 Serum hormone levels at C comparing Group A (CCI BID), B (CCI BID), C (CCI BID) with Group D (Placebo)
15. To assess the PK of orally administered OG-6219 and the active metabolite FOR-1011 using sparse and intensive ^c PK sampling.	
 Plasma concentrations of OG-6219 and FOR-1011 at scheduled assessments using sparse PK sampling during the treatment period. C_{max}, T_{max}, and AUC_{tau} for both OG-6219 and FOR-1011 on CCI for the population with intensive PK sampling
CCI	

CCI

Note: Refer below and to [Figure 1](#)

- Screening Cycle is between C and C.
 - Baseline Cycle is defined as CCI which starts at C (first day of the menses) and ends at one-day before next menses.
 - Treatment Cycle 1 is the period between the first day of menses associated with treatment start (C) to the day prior to the first day of next menses, regardless of number of days.
 - Treatment Cycle 2 is the period between the first day of second menses after end of BC to the day prior to first day of next menses, regardless of number of days.
 - Treatment Cycle 3 or EOT is the period between the first day of third menses after end of BC to either end after CCI on study treatment, whichever occurs first.
 - Safety Follow-up Cycle is the period time between the first day after stopping study treatment during TRC3 and ends after 30 consecutive days.
- a. OPP score is defined as the combination of the DYS and NMPP scores in a cycle
 - b. CCI
 - c. Intensive PK sampling is optional and applicable for subset of PK analysis set, where a separate consent would be provided.
 - d. Clinical significance is defined as any variation in physical findings or laboratory assessments that has medical relevance and may result in an alteration in medical care refer to [Section 8.3.1](#) and [Section 8.3.7](#).

Abbreviations:

AE=Adverse event;

CCI

BC=Baseline Cycle;

C-SSRS=Columbia-Suicide Severity Rating Scale;

CCI

DYS=Dysmenorrhea;

CCI
ECG=Electrocardiogram;
EHP-30=Endometriosis Health Profile-30;
CCI
CCI
NMPP=Non-menstrual pelvic pain;
CCI
PGI-S=Patient Global Impression of Severity;
SC=Screening Cycle;
CCI
TRC1=Treatment Cycle 1;
TRC3=Treatment Cycle 3;
V=Visit;
CCI

CCI
eDiary=Electronic diary;
EOT=End of Treatment;
ERP=Endometriosis-related pain;
CCI
NRS=Numeric rating scale;
OPP=Overall Pelvic Pain (endometriosis-related);
PGI-C=Patient Global Impression of Change;
PK=Pharmacokinetic;
CCI
TRC2=Treatment Cycle 2;
CCI

Overall Design:

This is a global multicenter, Phase 2a/b, randomized, double-blind, Placebo-controlled, 4-arm proof of concept, dose-range study to assess the efficacy, safety, and tolerability of 3 dose levels of OG-6219, in pre-menopausal women 18 to 49 years of age (inclusive), who have been surgically diagnosed with endometriosis within the last 4 months to 10 years prior to Visit 1 (V1) and with moderate to severe ERP.

The study duration of approximately 28 weeks includes: an initial period of approximately 2 to 4 weeks, between V1 and CCI to collect safety laboratory assessments. Each cycle refers to 1 menstrual cycle around 21 to 32-day duration. A Screening Cycle (SC), between CC and CCI; A BC or Single-blind CCI, between CC and CCI. A Randomization Visit (CC), to treatment allocation with a ratio of CCI to 3 active arms and 1 Placebo arm. This is a double-blind treatment cycle across 3 menstrual cycles, Treatment Cycle 1 (TRC1), Treatment Cycle 2 (TRC2), and Treatment Cycle 3 (TRC3) or End of treatment (EOT); and is followed by a Safety Follow-up Cycle (SFC). Overall, the study includes C on-site visits and C phone contacts, as detailed below:

- Screening Period:
 - One SC: Starts at CC (first day of the menses) and ends one-day before next menses.
 - One BC during the single-blind, CCI period: Starts at CC (first day of the menses) and ends at one-day before next menses.
- Randomization: CC, this is on first day of the next menses after the end of BC.
- Treatment Period: Three treatment cycles (TRC1, TRC2, and TRC3) after CC:
 - TRC1 is the period between the first day of menses associated with treatment start (CC) to the day prior to the first day of next menses, regardless of number of days. CCI

- TRC2 is the period between the first day of second menses after end of BC to the day prior to first day of next menses, regardless of number of days. Phone Contact **C** is done during the menses.
- TRC3 or EOT is the period between the first day of third menses after end of BC to either end after **C** completed cycles or **CCI** on study treatment, whichever occurs first.
- Safety Follow-up:
 - SFC, is the period of time between the first day after stopping study treatment during TRC3 and ends after 30 consecutive days (regardless of whether it aligns with first day menses or not). Phone contact **C** is done at **CCI** after last intake of study treatment. **CCI** at the first day of next menses is considered End of Study (EOS).

At **CC**, participants will receive the eDiary which will be used **CCI** until the EOS (**CC**) to collect the **CCI** (worst) pelvic pain scores (DYS, NMPP, dyspareunia). The pain score entered **CCI** by each participant in the eDiary must capture **CCI** corresponding to that day and should be entered at about the same time (before going to bed). The eDiary will also collect **CCI**

CCI as well as mental health assessment via C-SSRS will be collected according to the Schedule of Activities (SoA). Participants' safety will be continuously monitored by the Sponsor and by an external Data Monitoring Committee [DMC] committee throughout the study (at ongoing and pre-defined windows).

Number of Participants:

Approximately **CCI** pre-menopausal females aged 18 to 49 years old (inclusive), who have been surgically diagnosed with endometriosis within the last 4 months to 10 years prior to V1, will be screened to achieve 380 randomly assigned to study treatment (**C** participants per group). A minimum subset **CCI** per treatment group (including Placebo group) will be voluntarily enrolled for optional intensive PK sampling for the entire duration of the study.

Study Treatment Groups and Duration:

Treatment Arm	Treatment	Dose	Blinded Doses	Sample Size	Route of Administration	Regimen/ Treatment Period ^a	Use
CCI	OG-6219 CCI	CC BID	CCI BID (Bottle A) CCI BID (Bottle B)	N= C (minimum)	Oral	Single-blind Treatment Period CCI	CCI
OG-6219 CCI BID	OG-6219	CCI BID	CCI BID (Bottle A) CCI BID (Bottle B)	N= C	Oral	Double-blind Treatment Period CCI	Experimental
OG-6219 CCI BID	OG-6219	CCI BID	CCI BID (Bottle A) CCI BID (Bottle B)	N= C	Oral	Double-blind Treatment Period CCI	Experimental
OG-6219 CCI BID	OG-6219	CCI BID	CCI BID (Bottle A) CCI BID (Bottle B)	N= C	Oral	Double-blind Treatment Period CCI	Experimental
Placebo	OG-6219 Placebo	CC BID	CCI BID (Bottle A) CCI BID (Bottle B)	N= C	Oral	Double-blind Treatment Period CCI	Placebo

Abbreviations: BID=twice a day; V=visit.
^a Maximum treatment duration must not exceed CCI

Statistical Methods:

Efficacy:

The primary endpoint will be the mean change from BC of the average daily OPP score during TRC3. The OPP will be calculated for each cycle as the total of OPP scores reported during the cycle divided by the number of days during the cycle in which the score was reported. For participants who discontinue early, their last cycle will be associated with the cycle number at entry into the cycle. The primary analysis will be conducted using all participants with a post-treatment OPP measurement and will use a longitudinal model. The response vector for the model will be change from BC in the average OPP during TRC1, TRC2, and TRC3. Model terms will include the respective baseline, treatment, time (ie, cycle), and treatment-time interaction, allowing for the inclusion of individual outcomes over time (cycle). An unstructured error structure will be assumed. If nonconvergence is encountered, compound symmetry (CS) and first-order autoregressive AR(1) error structures will be considered.

Least squares mean change from baseline for each treatment group, with corresponding standard errors will be provided. Estimated treatment differences (each active treatment group versus Placebo) with corresponding 95% confidence intervals and 2-sided p-values will also be provided for each active treatment group. No missing data will be imputed for the primary analysis.

Supportive analyses will be conducted using an analysis of covariance (ANCOVA) on the change from baseline to the TRC3, with treatment as a fixed factor and baseline OPP as a covariate.

Secondary endpoints assessing change in continuous endpoints over time (either measurements within the cycle or at an individual visit) will use longitudinal models as described for the primary endpoint and/or ANCOVA models. Changes from SC to SFC will be compared using ANCOVA models using all participants with an OPP measurement during SFC. Select longitudinal models which focus on TRC1 and TRC2 may exclude TRC3 from the model. An unstructured error structure will be assumed for all longitudinal models. If nonconvergence is encountered, CS and AR (1) error structures will be considered.

Primary Safety Analysis:

The proportions of participants who experienced the following will be summarized

- A treatment-emergent adverse event (TEAE)
- Premature discontinuation of study treatment due to an AE
- Changes from baseline to EOS abnormalities in clinical laboratory assessments, vital signs, and physical and gynecological examination

Pharmacokinetics:

- PK analysis set: The PK analysis set is a subset of the Safety analysis set (SAF) and will include all participants who received at least 1 dose of OG-6219 and have at least 1 quantifiable OG-6219 concentration.
- PK analysis set for noncompartmental analysis: The PK analysis set for noncompartmental analysis (NCA) will include all participants in the PK analysis set who chose intensive PK sampling in Day 1 (CC) and CC. Intensive PK sampling is optional where a separate consent would be provided.

OG-6219 and its primary metabolite FOR-1011 concentrations (all participants receiving OG-6219) will be summarized by treatment, study visit, and scheduled time for the PK analysis set, as appropriate.

Pharmacodynamics:

- PD analysis set: The pharmacodynamic (PD) analysis set is a subset of the SAF and will include all participants who received at least one dose of OG-6219 or Placebo and have at least 1 post-dose evaluable PD endpoint without protocol deviations or events affecting the PD results.

The PD and exploratory endpoints and change from baseline results will be summarized by treatment and scheduled time, where appropriate, for the PD analysis set.

Interim analysis (IA):

There will be no IA CCI. An interim psychometric analysis using blinded data will be performed to affirm methods for establishing pain responder cutoffs.

Data Monitoring/Other Committee: Yes

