 - Note: Hormonal contraception is not permitted in the study. Women of childbearing potential must use adequate non-hormonal contraceptive methods to prevent pregnancy. Contraception must be used throughout the study starting at V1 through to CCI. The sporadic use of emergency contraception is permitted during the study. Refer to the Appendix 5 to review the non-hormonal contraceptives method for this study.
 - f) Not planning to relocate during the study (such that the participant would not be able to continue participation at the study site).
9. Must be willing and able to provide signed informed consent before any study-related activities.

At Visit C: Inclusion Eligibility Criteria:

10. Has moderate to severe ERP, determined by the NRS (0 to 10 anchored, with 0 [no pain] and 10 [extremely severe pain]), at CCI (before Randomization), based on the eDiary entries from the participant's last menstrual cycle (BC), as follows:
- a) An OPP (DYS and NMPP) CCI, OR
 - b) For DYS at least 2 days with CCI, OR CCI, OR
 - c) For DYS at least 2 days with CCI (not necessarily consecutive).
11. Has demonstrated compliance with CCI of eDiary entries (ie, pelvic pain score, vaginal bleeding, rescue medication intake) during both the SC and the BC.
- Note: eDiary compliance will be automatically calculated by the eDiary vendor portal and a report will be provided. The Investigational study site should review the report before the participant's schedule visit to assess eligibility at Randomization Visit CCI.
12. Is CCI compliant with the Placebo tablets over the BC (CCI), as determined by tablet accountability at the site.
13. Has taken only the study provided rescue medication, at a dose not exceeding the maximum dose determined by the Investigator, for control of ERP during the BC as evidenced in the eDiary.
- CCI
14. Have a negative pregnancy test as outlined in the SoA (Section 1.3).

* Please contact the Medical Monitor surrounding non-binary participants eligibility in the clinical study.

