Appendix 6 Protocol-Specific Rescue Medication

The rescue medication will be naproxen sodium, CCI (administered per local guidelines) and will be provided by the Sponsor. The rescue medication is to be prescribed as per Investigator's discretion.

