#### 8.2.5. Prior, Concomitant, and Post-Treatment Medications

Medications entered in the Medical History form of the eCRF will be presented for the Safety Analysis Set and coded using WHO-Drug dictionary, September 2022 or later. In the case where it is not possible to define a medication as prior, concomitant, or post-treatment, the medication will be classified by the worst case, i.e., concomitant.

- ‘Prior’ medications are defined as any medications started prior to the day of the first dose of randomized study treatment.
- ‘Concomitant’ medications are defined as any medications taken on the day of or after the first dose of randomized study treatment and before or on the day of last

dose of randomized study treatment.

- 'Post-Treatment' medications are defined as any medications started after the day of last dose of randomized study treatment

Prior, concomitant, and post-treatment medication use will be summarized separately by preferred name using frequencies and percentages. Medications will be sorted alphabetically by Anatomical Therapeutic Chemical (ATC) Level 3 and preferred name in summaries.

Participants with multiple occurrences of a medication in the same ATC Level 3 or preferred name will only be counted once within the PT for each summary. If a medication is unable to be categorized to ATC Level 3, the most detailed level available will be used. The type of medication (Prior/Concomitant) will be indicated in the listing of all medications.

The use of prohibited pain medication registered in the eDiary will be summarized by treatment and treatment cycle for the MFAS. All use of prohibited pain medication will be listed in detail.

Use of supplied rescue medication for management of endometriosis related pain, that was reported in the eDiary as an efficacy endpoint, will not be included in the summaries and listings described above.

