### 8.3. Analyses Supporting Primary Efficacy Objective

#### 8.3.1. Efficacy assessments

Participants will complete the efficacy assessments in the **CCI** eDiary in the order presented

below:

- Vaginal bleeding pattern
- Endometriosis-related pain NRS for OPP (including vaginal bleeding)
- Dyspareunia
- Interference with daily activities
- Rescue medication use and number of tablets
- Prohibited pain medication use and reason

HRQoL and Productivity Questionnaires are conducted at Study visits per SoA:

- PGI-S
- PGI-C
- EHP-30
- WPAI-Endometriosis
- PROMIS Fatigue Short Form 6a
- EQ-5D-5L

Participants will complete eDiary items **CCI** asking about the severity of their worst pain over the last 24 hours on 11-point NRS for endometriosis-related pain. Endometriosis-related pain severity will be provided based upon an NRS from 0 (no pain) to 10 (worst pain imaginable) where lower value represents a better outcome.

**CCI** DYS is defined as the NRS endometriosis-related pain severity entered on a menstrual bleeding day, and **CCI** NMPP is defined as the NRS endometriosis-related pain severity entered on a non-menstrual bleeding day. **CCI** OPP is defined as the NRS endometriosis-related pain severity entered on any day regardless of menstrual bleeding (i.e. one cycle of **CCI** OPP scores consists of **CCI** DYS scores and **CCI** NMPP scores for the cycle).

The definition for a menstrual bleeding day used in the determinations for **CCI** DYS and **CCI** NMPP will be based upon bleeding information collected from the **CCI** diary for the two questions below:

- (1a) During the past 24 h did you have any vaginal bleeding or spotting?

- (1b) During the past 24 h have you been on your period?

If both questions are answered “Yes”, then that day qualifies as a menstrual bleeding day and the pain score is DYS. If either question is answered “No”, then that day is a non-menstrual bleeding day and the pain score is NMPP. OPP score is defined as DYS for menstrual bleeding days and as NMPP for non-menstrual bleeding days.

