#### RESCUE MEDICATION USE FOR ERP

Participants will be asked daily whether they used the rescue medication in the past 24 hours to treat their ERP. If yes, then number of tablets will be documented.

The secondary efficacy variables of rescue medication use for ERP are:

- Change from BC to TRC1, TRC2, and TRC3 in the mean number of tablets of rescue medication taken for ERP
- Change from BC to TRC1, TRC2, and TRC3 in the proportion of days participant has taken rescue medication for ERP

The mean number of tablets of rescue medication for ERP will be calculated for each cycle as the total number of tablets of rescue medication for ERP reported during the cycle, divided by the number of days during the cycle when a value was reported.

The proportion of days participant has used rescue medication for ERP will be calculated for each cycle as the total number of days participant has used ANY rescue medication for ERP, divided by the number of days during the cycle when a value was reported.

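### Both rescue-medication endpoints count only sponsor-supplied naproxen, so a treatment-cycle day on which only another analgesic is taken for endometriosis pain scores as rescue-free

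*Protocol*

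**What the plan says.** **What is counted.** Objective 4 (Protocol 1.1 and Table 1) is "To evaluate the daily use of Sponsor provided rescue medication taken for ERP at TRC1, TRC2, and TRC3". Appendix 6 of the protocol identifies the product: "The rescue medication will be naproxen sodium". SAP 8.4.1 describes the diary item in the same terms: "Participants will be asked daily whether they used the rescue medication in the past 24 hours to treat their ERP". The tablet endpoint is rescue tablets reported in the cycle over days with a reported value. The proportion endpoint has as numerator the "total number of days participant has used ANY rescue medication for ERP", over the same kind of denominator.

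**Other analgesics.** These are a separate eDiary item in SAP 8.3.1, "Prohibited pain medication use and reason". The word ANY in the proportion endpoint therefore does not bring them in.

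**Restriction before randomisation.** Inclusion criterion 13 (Protocol 5.1) requires, for control of ERP during BC, that the woman "Has taken only the study provided rescue medication, at a dose not exceeding the maximum dose determined by the Investigator", as shown in the eDiary.

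**Restriction after randomisation.** Protocol Table 2 and Section 6.8.2 keep other analgesics prohibited during participation. Section 7.2 lists inability to comply, including with the rules on rescue and prohibited medication, among the reasons for discontinuation. SAP 8.1.6 does not treat prohibited pain medication as an intercurrent event.

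**Analyses.** SAP 8.3.6 repeats the primary analysis without the overall pelvic pain (OPP) scores from prohibited-medication days. SAP 8.4.3 extends similar sensitivity analyses to dysmenorrhea (DYS) and non-menstrual pelvic pain (NMPP). For the rescue endpoints, 8.4.3 refers only to 8.3.5 (the MMRM) and 8.3.7 (the ANCOVAs). SAP 8.2.5 adds: "The use of prohibited pain medication registered in the eDiary will be summarized by treatment and treatment cycle for the MFAS".

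**The concern.** A fall in rescue use is naturally read as less need for analgesia. That reading holds only if rescue use stands for all analgesia taken for ERP at both ends of the change score. In BC criterion 13 makes this nearly so. During treatment it depends on adherence to a prohibition, and the SAP expects some departures because it sets out how to handle them.

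A woman who replaces study naproxen with another drug on some days is scored as having improved. The error has one direction: substitution can lower the scored value but cannot raise it. Within-arm changes are then too favourable. The comparison with placebo is affected when one arm substitutes more. If that arm is placebo, a real benefit is diluted; if it is a dose arm, an apparent benefit is created. The SAP takes prohibited-medication days seriously enough for a sensitivity analysis of the pain scores, yet has none for the endpoints where substitution acts directly on the numerator.

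**Working it through.** **Plan's own figure.** The documents give no SD, effect size or power for the rescue endpoints, so there is nothing to reproduce. The 84% power in SAP 4.3 concerns mean OPP (1 point, SD 2.2, 95 per group, 10% dropout) and does not bear on this point.

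**Scoring rule (SAP 8.4.1).** Proportion = rescue days / days reported. Tablets = rescue tablets / days reported.

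- Naproxen only: the day counts and its tablets count.
- Naproxen and another analgesic: the day counts, but only the naproxen tablets count.
- Another analgesic only: the day enters the denominator with no rescue and 0 tablets.
- Neither drug: scored identically to the previous line.

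**One woman.** Assumptions, not from the documents: 28 reported days per cycle; 8 ERP analgesic days in BC, all naproxen; still 8 in TRC3, of which 3 are with another drug alone.

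- BC: 8/28 = 28.6%
- TRC3 as scored: 5/28 = 17.9%
- Scored change: -3/28 = -10.7 points
- True change in ERP analgesic days: 8/28 - 8/28 = 0
- Tablets, at an assumed 2 per rescue day: -(3 x 2)/28 = -0.21 per day

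**Within-arm range.** With *b* analgesic days unchanged between cycles and a share *s* of them moved to another drug alone, the scored change is -100 x b x s/28 points:

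| b | s = 10% | s = 25% | s = 50% |
|---|---|---|---|
| 6 | -2.1 | -5.4 | -10.7 |
| 10 | -3.6 | -8.9 | -17.9 |
| 14 | -5.0 | -12.5 | -25.0 |

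**Between arms.** Spurious difference, dose minus placebo = 100 x (b/28) x (s_placebo - s_dose).

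- Equal shares, such as 10% in each arm: 0 for every *b*.
- 5% on the dose and 25% on placebo: +4.3, +7.1 and +10.0 points for b = 6, 10 and 14, against the dose.
- Shares reversed: the same sizes with the opposite sign, in favour of the dose.

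**Would the 8.3.6 exclusion serve instead?** Take the same woman and drop her 3 other-drug days. TRC3 becomes 5/25 = 20.0%, and the change is 20.0 - 28.6 = -8.6 points. Excluding days on which analgesia was needed removes little of the error. Counting those days gives (5 + 3)/28 = 28.6% and a change of 0.

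**The case against.** The strongest reply is that the endpoint does what its objective says. Objective 4 names sponsor-provided medication, and SAP 8.4.1 implements that faithfully, so there is no derivation error. This stands, and it is why the protocol endpoints should remain as they are.

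Second, the SAP has considered prohibited analgesics. Section 8.1.6 argues that effects must be judged in their presence, and 8.2.5 tabulates their use by arm and cycle and lists it in detail. A reader could therefore see a marked imbalance. But the table as specified is not combined with rescue days within a woman, not restricted to ERP as the reason, and not expressed as a change from BC, so it cannot correct the endpoint.

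Third, a reader might infer that the bar on other analgesics lapses at randomisation. The documents do not support that: Table 2 and Section 6.8.2 of the protocol continue it, and Section 7.2 backs it with possible discontinuation. The difference is between a condition of entry and an ongoing prohibition whose breaches otherwise stay in the data.

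Fourth, some protocol text on other analgesics is redacted (after criterion 13, in 6.8.2, in 8.2.2 and in the Appendix 8 heading). Any permitted limited use, and the response options of the reason field, cannot be seen. This leaves the scoring rule untouched but limits certainty about how complete the baseline is and whether ERP can be identified as a reason.

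**Conclusion.** The point holds as a gap in the supportive analyses. On the visible text, a treatment-cycle day with only a non-study analgesic for ERP scores as rescue-free, and no planned analysis of the rescue endpoints corrects for it. Within-arm changes are biased towards improvement to whatever extent substitution occurs: -10.7 points in the single-woman example, and -2.1 to -25.0 points over the assumed range of 6 to 14 analgesic days and 10% to 50% substitution. Those inputs are illustrative; the documents give no substitution rate.

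Two stronger readings should be resisted. One is that the dose-placebo comparison is biased as planned: it is biased only if substitution differs by arm, and equal substitution cancels. The other is a stated loss of power: without an SD or effect size for rescue use, any such figure would be borrowed from the OPP calculation.

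The priority is low to moderate. These are secondary endpoints with nominal p-values and no multiplicity control (SAP 8.1.7), and the remedy is a cheap improvement.

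**What to change.** In SAP 8.4.1, define a supportive variable: the proportion of reported days in the cycle with study rescue medication, or with other pain medication whose eDiary reason is ERP. If ERP cannot be identified from the reason field, count other pain medication for any reason and say so. Derive it identically in BC and in each treatment cycle; this matters most for the any-reason version, because criterion 13 restricts BC use for ERP only.

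In SAP 8.4.3, analyse its change from BC with the same MMRM and show it beside the two protocol endpoints, which stay unchanged. State that the tablet endpoint is to be read in light of this result, since tablets of different drugs cannot simply be added. Do not rely on the day-exclusion approach of 8.3.6 here. Specify the analysis before unblinding; if that is no longer possible, label it post hoc, as SAP Section 2 requires.

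The cost is one derived variable and one table from eDiary items already collected, subject to the reason field being usable. The downside is an extra result that may be less favourable than the rescue-only figure. No treatment rule changes.
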